9.1. Adverse Events

Adverse events are collected from signing of the informed consent form through the end of follow-up. Adverse events will be coded to the preferred terms of the Medical Dictionary for Regulatory Activities (MedDRA®, version 24.1).

A treatment-emergent adverse event (TEAE) will be defined as any AE that begins on or after the date of first dose of study drug up through 14 days after the date of last dose of study drug. AEs that begin more than 14 days after the date of last dose of study drug and AEs that begin during the period from obtaining informed consent to the start of administration of study drug will not be considered treatment-emergent and will be listed only.

The following AE summaries will be provided for each treatment period:

- TEAE overall summary
- TEAEs by preferred term
- TEAEs by system organ class and preferred term
- Moderate or severe TEAEs by system organ class and preferred term
- TEAEs by preferred term with frequency > 3% of safety analysis set subjects
- TEAEs by system organ class, preferred term, and severity
- Drug-related TEAEs by system organ class and preferred term
- Drug-related TEAEs by system organ class, preferred term, and severity
- Drug-related moderate or severe TEAEs by system organ class and preferred term
- Serious TEAEs by system organ class and preferred term
- Drug-related serious TEAEs by system organ class and preferred term
- TEAEs resulting in on-study deaths
- TEAEs leading to premature study drug discontinuation
- TEAEs leading to temporary interruption of study drug
- TEAEs of special interest by system organ class and preferred term (Section 9.1.1)

If no adverse events meeting a specific table definition were reported, the body of the table will contain only a statement that no events met the table definition.

The following AE listings will be provided:

- TEAEs
- AEs leading to premature study drug discontinuation
- AEs resulting in temporary interruption of study drug
- Serious adverse events
- Deaths
- Non-treatment-emergent adverse events
- Adverse events of special interest (Section 9.1.1)
- Adverse events for excluded site 27045 (Section 6.2.1)

9.1.1. [REDACTED]

[REDACTED]

- [REDACTED]
- [REDACTED]
- [REDACTED]
- [REDACTED]
- [REDACTED]
- [REDACTED]

[REDACTED]

9.2. Extent of Exposure and Treatment Compliance

Duration of study drug exposure (days) will be summarized. Duration of exposure to study drug is calculated as (date of last dose – date of first dose + 1).

Subjects will take their assigned study medication once daily.

Treatment compliance as a percentage of the expected total dose will be calculated as follows, using the information captured on the CRF page for “Study Drug Dispensing / Return”:

$$100 \times (\text{number of tablets dispensed} - \text{number returned}) / (\text{date of last dose} - \text{date of first dose} + 1)$$

Treatment compliance as a percentage of expected total dose will be summarized as a continuous variable and using the following categories, after rounding to the nearest 0.1%:

- $\geq 120\%$
- $\geq 80\% - < 120\%$
- $< 80\%$

Study drug administration (date/time and study day) and drug accountability data will be listed.

9.3. Concomitant and Other Medications

Medications will be coded using the World Health Organization Drug Dictionary (WHODD, version 1Q 2021 C3). Medications entered on the case report form will be mapped to Anatomic Therapeutic Chemical (ATC) drug class and generic drug name. Each verbatim name will be classified by anatomical main group (ATC level 1), therapeutic subgroup (ATC level 2), pharmacological subgroup (ATC level 3), chemical subgroup (ATC level 4), and preferred name (ATC level 5, chemical substance).

Prior medications are medications taken before the first dose of study drug. Concomitant medications are medications taken after the first dose up through 14 days after the last dose, and include ongoing prior medications.

The number and percentage of subjects receiving prior medications, the number and percentage receiving concomitant medications, and the number and percentage receiving prohibited concomitant medications will be summarized by medication class and standardized medication name (preferred name). If available, ATC level 4 will be used to determine the medication class. If ATC level 4 is not available, the next available level of ATC code (i.e., level 3, level 2, or level 1) will be used. Subjects reporting use of more than one medication at each level of summarization (any medication received, ATC class, and preferred name) will be counted only once.

All medications will be listed.

On-treatment midodrine usage will be summarized by providing a categorical summary of number of uses and descriptive summaries (n, mean, SD, etc.) of usage rate (uses/month), calculated as (number of uses)/(treatment period duration in days, divided by 28) and total dose (mg). For number of uses, counts and percentages will be provided for the following categories:

- 0
- 1
- 2
- 3
- 4
- 5
- 6 – 10

- 11 – 20
- > 20

A use is defined as taking 1 or more 2.5-mg midodrine tablets on a single occasion, e.g., 2 tablets taken at 0900 and 2 tablets taken at 1200 = 2 uses, for a total daily dose of 10 mg.

9.4. Laboratory Data

Laboratory data hematology and serum chemistry summaries will include summary statistics for observed values and for changes from baseline at each postdose visit. In addition, changes from baseline for each visit relative to normal ranges (e.g., shifts from normal to abnormal high/low) will be summarized in shift tables for hematology and serum chemistry test results. Urinalysis data will be listed only.

Listings will flag laboratory values that are outside the normal range.

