6. Subject has known or suspected alcohol or substance abuse within the past 12 months (Diagnostic and Statistical Manual of Mental Disorders, Fourth Edition, Text Revision [DSM-IV-TR[®]] definition of alcohol or substance abuse).
7. Subject has a clinically unstable coronary artery disease or has had a major cardiovascular or neurological event in the past 6 months.
8. Subject has used any monoamine oxidase inhibitor (MAO-I) within 14 days prior to V1.
9. Subject has a history of untreated closed angle glaucoma, or treated closed angle glaucoma that, in the opinion of an ophthalmologist, might result in an increased risk to the subject.
10. Subject has any significant uncontrolled cardiac arrhythmia.
11. Subject has a Montreal Cognitive Assessment (MoCA) ≤ 23 .
12. Subject is unable or unwilling to complete all protocol specified procedures including questionnaires.
13. Subject had a myocardial infarction in the past 6 months or has current unstable angina.
14. Subject has known congestive heart failure (New York Heart Association [NYHA] Class 3 or 4).
15. Subject has had any malignant disease, other than carcinoma in situ of the cervix or basal cell carcinoma, within the past 2 years prior to screening.
16. Subject has a known gastrointestinal (GI) condition, which in the Investigator's judgment, may affect the absorption of study medication (e.g., ulcerative colitis, gastric bypass).
17. Subject has psychiatric, neurological, or behavioral disorders that may interfere with the ability of the subject to give informed consent or interfere with the conduct of the study.
18. Subject is currently receiving any investigational drug or has received an investigational drug within 30 days of dosing. An investigational drug is defined as drug that is not approved by a regulatory agency (e.g., Food and Drug Administration [FDA]).

19. Subject has a clinically significant abnormal laboratory finding (e.g., alanine aminotransferase [ALT] or aspartate aminotransferase [AST] >3.0 x upper limit of normal [ULN]; blood bilirubin [total] >1.5 x ULN; estimated glomerular filtration rate (eGFR) <30 mL/min/1.73 m², or any abnormal laboratory value that could interfere with safety of the subject).
20. Subject has demonstrated a history of lifetime suicidal ideation and/or suicidal behavior, as outlined by the C-SSRS (Baseline/Screening Version). Subject should be assessed by the rater for risk of suicide and the subject's appropriateness for inclusion in the study.

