8.6.4. Laboratory Data

Laboratory values, changes from baseline, values relative to normal ranges, and values and changes meeting specified criteria, will be summarized by nominal visit.

Reference ranges provided by the laboratory for each test will be used to evaluate the clinical significance of laboratory test results. Values falling outside the relevant reference range will be flagged, as appropriate, in the data listings. Abnormalities in clinical laboratory test results will be listed in a separate listing.

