11.2. Changes to Protocol-Specified Analyses

- Removal of smoking status subgroups
- Addition of baseline norepinephrine subgroups
- To the planned analyses of standing SBP at 3 minutes and at 10 minutes during the orthostatic standing test, addition of similar analyses of standing heart rate at 3 minutes and at 10 minutes

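### SAP 9.4 omits, without declaring it, the protocol's summary of laboratory values meeting specified criteria, so no table counts subjects with marked abnormalities by group

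*SAP*

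**What the plan says.** Protocol 8.6.4 names four laboratory summaries in one sentence: "Laboratory values, changes from baseline, values relative to normal ranges, and values and changes meeting specified criteria, will be summarized by nominal visit". It does not say what the specified criteria are. Protocol 8.1 says that changes to the planned summaries will be described in the SAP.

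SAP 9.4 gives, for hematology and chemistry, "summary statistics for observed values and for changes from baseline at each postdose visit", followed by normal-range shifts: "shifts from normal to abnormal high/low) will be summarized in shift tables for hematology and serum chemistry test results". For listings it says "Listings will flag laboratory values that are outside the normal range", and for urine tests "Urinalysis data will be listed only". Section 9 of the SAP applies all safety summaries separately to the open-label and randomized withdrawal periods.

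SAP 11.2 lists three changes to protocol-specified analyses. The first is "Removal of smoking status subgroups"; the others add baseline norepinephrine subgroups and standing heart rate analyses. None concerns laboratory data.

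**The concern.** A shift table built on the normal range has one high cell and one low cell per test. It shows how many subjects left the normal range, not how far they went. For liver enzymes, renal function and electrolytes, the distance is usually what matters. Protocol 1.4 names hyponatremia among the possible risks, and sodium is in the chemistry panel; a slightly low and a severely low sodium would share one cell.

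Safety and tolerability over up to 22 weeks is one of the two primary objectives (Protocol 2.1, SAP 3.1.1). Vital signs and ECGs both keep counts of subjects beyond stated limits (SAP Tables 9 and 10). Laboratory data have no equivalent, although the protocol says that criteria would be applied to them too.

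**Working it through.** There is no figure in the plan to reproduce. The check sets the two documents side by side and then follows a marked value through the SAP rules.

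**1. Component by component**

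| Protocol 8.6.4 | SAP 9.4 |
|---|---|
| Values | Present (hematology, chemistry) |
| Changes from baseline | Present (hematology, chemistry) |
| Values relative to normal ranges | Present, as shift tables |
| Values and changes meeting criteria | Absent |

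Three of four are carried over. Two smaller differences are also undeclared. Urinalysis is listed only, and the separate listing of abnormal results in Protocol 8.6.4 becomes a flag in the SAP listings.

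**2. Could the missing piece be elsewhere in the SAP?** Section 9.4 has no redacted text. The two hidden entries in the SAP list of tables lie between Table 5 and Table 8, within the outcome-scoring material of Section 8.8. Section 11.1.4 deals with missing laboratory baselines, retests and detection limits, not with severity. The SAP's heading for adverse events of special interest (9.1.1) is redacted beneath, but the events listed in Protocol 7.1.4 include no laboratory abnormality. Table shells were not available, and SAP 9.4 does not refer to any for laboratory criteria.

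**3. What the shift table does with magnitude.** Take two assumed ALT results, 1.1 and 10 times the upper limit of normal (ULN), each from a normal baseline. Both exceed 1 x ULN, so both count once in the normal-to-high cell.

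**4. What happens to an off-schedule peak.** SAP Table 3 gives laboratory tests a single postbaseline window in the randomized period. It is labelled Week 22 and runs from the first randomized dose (day DD) to end of study, with nominal day DD+41. SAP 6.5.1 keeps the record closest to nominal. Suppose an unscheduled ALT peak on DD+20 and a scheduled result on DD+41 (assumed days):

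- distance of the peak: |20 − 41| = 21 days
- distance of the scheduled result: |41 − 41| = 0 days

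The scheduled result is kept, and the peak enters neither the descriptive statistics nor the shift table. The same rule applies within the three open-label windows (Weeks 2, 8 and 16). Protocol 8.6 leads to the same place, since it leaves unscheduled quantitative results out of summaries.

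**5. What remains visible**

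- *Visit maximum:* the default eight-statistic summary in Protocol 8.1 includes minimum and maximum. That is one extreme per visit and column, with no count of subjects.
- *Listings:* individual values are shown and flagged as outside normal, with no flag for magnitude and no count.
- *Adverse events:* Protocol 7.2 requires abnormalities that are symptomatic or judged clinically significant to be recorded if they meet the event definition. SAP 9.1 then tabulates them, and SAP 6.1 supplies placebo and TD-9855 columns for the randomized period. This is by arm, but it depends on each investigator's judgment.

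**The case against.** The strongest reply is that the safety reader is well served without this table. Laboratory changes the investigator considers important reach the adverse event tables by arm, with breakdowns by severity, seriousness, relatedness and discontinuation. The visit maximum would show a very high value, provided its record is the one kept. A reader might therefore be tempted to say that only a listing is left and that nothing is compared between arms. The documents do not support that: the descriptive, shift and adverse event tables all have treatment columns in the randomized period.

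The reply is also right that no defined analysis was taken away. One might infer that a laboratory threshold table was deleted, but the protocol's list of tables has only the visit schedule, vital signs and ECG. The protocol left its criteria unspecified, and the SAP did not fill the gap.

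Nor does the protocol supply ready-made limits. De Novo exclusion criterion 19 mentions ALT or "aspartate aminotransferase [AST] >3.0 x upper limit of normal [ULN]; blood bilirubin [total] >1.5 x ULN", and an eGFR limit, as examples of abnormal findings at entry. These are not safety-analysis criteria. The important potential risks named in Protocol 1.4 are heart rate, blood pressure and syncope, and the first two have threshold tables.

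These points limit the weight of the concern but do not answer it. Adverse event reporting does not apply a uniform numeric rule, a maximum is not a count, and the protocol commitment remains unmet and undeclared.

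**Conclusion.** The point holds in a limited form. One of four laboratory summaries named in the protocol is absent from SAP 9.4 in both periods, and SAP 11.2 is silent although Protocol 8.1 calls for such changes to be described. Following the SAP as written, no table counts, by group, the subjects crossing a uniform laboratory threshold, and an off-schedule peak can drop out of the summaries.

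The gap affects the reporting of a primary safety objective. It does not touch the primary efficacy analysis or the error rate. In the open-label period the columns are entry groups, so the missing counts there would be descriptive, with no concurrent control. The documents give no laboratory event rate, so nothing can be said about how many subjects would be involved. The conclusion assumes that unseen table shells do not already contain laboratory criteria; if they do, the remedy is to state them in the SAP.

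**What to change.** In SAP 9.4, define analysis criteria for key hematology and chemistry tests: for example, multiples of ULN for ALT/AST and bilirubin, and limits for eGFR and sodium. The figures in exclusion criterion 19 may serve as a starting point only; the SAP should state its own.

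Present counts and percentages of subjects meeting each criterion, using the SAP 6.1 columns, for each period, by visit and at any postbaseline time. State that unscheduled results count toward the any-time row, since SAP 6.5.1 and Protocol 8.6 would otherwise leave many of them out. In the randomized period there is only one laboratory window, so the any-time row is the one that adds information.

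If the sponsor prefers not to produce the summary, SAP 11.2 should say so and give the reason. The urinalysis and abnormality-listing differences should be declared there in either case.

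The cost is one extra table per period, two in all, from data already collected. No protocol amendment or new assessment is needed.

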9.5. Vital Signs and Weight

Weight and vital signs (HR and systolic and diastolic BP) and their changes from baseline at postbaseline visits will be summarized. (Following the start of the open-label treatment period, weight is collected at the beginning and end of the randomized withdrawal treatment period and at the 10-day follow-up visit.) At visits when orthostatic standing test results are collected, the vital signs (BP and HR) collected after 10 minutes supine and 10 minutes seated from the orthostatic standing test will be used for these summaries. Therefore, the BP and HR summaries for these visits will include body position (supine and seated). At Visit 2 (Day 15), which does not include an orthostatic standing test, the position in which BP and HR were collected is not recorded. Visit 2 measurements will be assumed to have been collected while the subjects were seated.

The counts and percentages of subjects with vital signs in the ranges shown in [Table 9](#) will be presented in an extreme values summary. Extreme values will be flagged in the listing.

Table 9: Vital Signs Extreme Value Thresholds

Heart Rate (bpm)	Systolic Blood Pressure (mmHg)	Diastolic Blood Pressure (mmHg)
< 40	< 85	< 45
> 110	> 160	> 100

9.5.1. Ambulatory Blood Pressure

Ambulatory blood pressure monitoring equipment will be provided to subjects during the screening visit. Beginning approximately 72 to 24 hours before subjects return to the clinic on Day 1 (Visit 2), and before the Day 8 and Day 22 visits, subjects will put on the 24-hour blood pressure monitoring equipment and initiate the recording. Once the 24-hour session is complete, subjects will remove and return the equipment to the research center during the next visit. During

each 24-hour session, the BP monitoring device will be programmed to automatically measure BP every 2 hours beginning at the top of the hour. During each 24-hour session, subjects should also maintain a log of their posture at the time of each BP measurement.

ABPM position and body position time points will be matched using a ± 10 minutes window. If there is more than 1 body position time point within the window, the position time point closest to the ABPM time point will be used. If there is a tie, the earlier position time point will be used.

SBP, DBP, and HR in the supine position from ABPM will be summarized for 24-hour, daytime (8am–4pm), and nighttime (11pm–5am) average by treatment and visit. Assessments in other positions will be listed.

9.6. 12-Lead Safety ECGs

ECG summaries will include summary statistics for observed values and changes from baseline. Heart rate and the following intervals will be included: PR, QRS, QT, and QTcF. A listing of 12-lead safety ECG data collected will be provided. A separate listing of data for subjects with postbaseline values of QTcF ≥ 500 msec or a QTcF increase from baseline > 60 msec will also be provided.

Investigator Assessment of ECG Readings

The investigator's assessment of ECGs as normal, abnormal and clinically significant, or abnormal but not clinically significant will be summarized by visit.

Categorical ECG Summary

QTcF (msec) will be summarized by the following categories: Normal (males < 430 , females < 450), Borderline (males $[\geq 430, < 450]$, females $[\geq 450, < 470]$), and Prolonged (males ≥ 450 , females ≥ 470).

The number of subjects with absolute ECG values and changes from baseline in the ranges shown in [Table 10](#) will be presented by visit.

Table 10: ECG Thresholds and Ranges

Heart Rate (bpm)	Heart Rate Change from Baseline (bpm)	PR Interval (msec)	PR Percent Change From Baseline	QRS Interval (msec)	QT _c F (msec)	QT _c F Change From Baseline (Msec)
> 120	≥ 20	≥ 200	≥ 15%	≥ 120	Males:	≤ 30
> 130	≥ 30	≥ 220	≥ 25%		< 430	> 30, ≤ 60
					≥ 430	> 60
					≥ 450	
					≥ 470	
					≥ 480	
					≥ 500	
					Females:	
					< 450	
					≥ 450	
					≥ 470	
					≥ 480	
					≥ 500	

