8. STATISTICAL CONSIDERATIONS

8.1. General Considerations

All data for each subject will be listed as collected. All statistical summaries and analyses will be performed using SAS software (SAS Institute, Cary, North Carolina, US).

Continuous data will be summarized using an 8-point descriptive summary (n, mean, standard deviation, median, interquartile range [25% quartile, 75% quartile], minimum, and maximum) unless otherwise specified in the statistical analysis plan (SAP) or table shell. Categorical data will be summarized using counts and percentages.

For analysis, Day 1 is defined as the day of the first study medication dose. The preceding day is Day -1.

Baseline is the last assessment (scheduled or unscheduled) obtained before start of study medication dosing for each phase of the study (OL or double-blind randomized withdrawal phase), unless otherwise specified in the SAP. Baseline for endpoints that have more than one component is calculated from the individual component baselines, whether or not they were assessed during the same visit.

Any changes to the data summaries and analyses outlined in this section will be described in the applicable SAP. Any changes to the definition of the endpoints will also be included in a protocol amendment.

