8.6. Safety Analyses

Safety data, including C-SSRS, will be descriptively summarized separately for OL phase and double-blind randomized withdrawal phase.

The OL phase data will be summarized for all subjects and by enrollment group (De Novo Group or 0169 Completers Group), and the double-blind randomized withdrawal phase data will be summarized by treatment group according to treatment subjects received. Quantitative data collected at unscheduled times will be listed but will not be included in summaries. Categorical data collected at unscheduled times (e.g., ECG finding categories) will not be included in summaries by time point but will be included in summaries of findings during the entire treatment period.

Safety analyses will be performed using the safety analysis set. Unless specified otherwise, there will be no imputation of missing data in safety summaries. Subjects without post baseline measurement (e.g. ECG or vital signs) for a given time point will be excluded from the summary statistic (e.g., denominator of the summary statistic) for that time point.

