8.6.6. Electrocardiogram Data

The QTcF, PR interval, QT interval, QRS duration, and HR from standard digital ECGs will be summarized in terms of observed values, changes from baseline, and counts and percentages within appropriately defined categories.

Table 3: Electrocardiogram Test Outlier Thresholds

Heart Rate (bpm)	Heart Rate Change From Baseline (bpm)	PR Interval (msec)	PR Percentage Change From Baseline (%)	QRS Interval (msec)	QT _c F (msec)	QT _c F Change From Baseline (msec)
>120	≥20	≥ 200	≥ 15	≥ 120	Males:	≤ 30
>130	≥30	≥ 220	≥ 25		< 430	>30, ≤ 60
					≥ 430	> 60
					≥ 450	
					≥ 470	
					≥ 480	
					≥ 500	
					Females:	
					< 450	
					≥ 450	
					≥ 470	
					≥ 480	
					≥ 500	

In addition, QT_cF (msec) will also be summarized by the following categories: Normal (males <430, females <450), Borderline (males [≥430, <450], females [≥450, <470]), and Prolonged (males ≥450, females ≥470).

All recorded ECG interval values and ECG assessments will be presented in a by-subject listing. A separate listing of subjects with extreme values or changes, as specified in the SAP (e.g., values of QT_cF ≥450 msec if male or ≥470 msec if female, QT_cF increases from baseline >60 msec) will be provided.

Treatment-emergent ECG abnormalities are defined as those not present at baseline, or those that worsened after treatment, e.g., borderline at baseline but were prolonged after treatment.

When multiple values exist for the same nominal time point (e.g., triplicate reading), the average of the readings taken for ECG parameters will be used in the data analysis, including the outlier analysis stated below.

Cumulative distribution plots will be provided for maximum change in QT_cF by day.

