6. CONSIDERATIONS FOR DATA ANALYSES AND HANDLING

All data from both scheduled and unscheduled visits will be presented in data listings.

However, unless noted otherwise, only data from visits (scheduled or unscheduled) that fall within analysis windows will be included in summaries, statistical analyses, and calculation of derived variables. [REDACTED] 5.

Analyses and tabulations will be prepared [REDACTED]

Summary tables and listings will be prepared according to ICH Guideline E3 and will include a “footer” providing explanatory notes.

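### SAP 9.6 omits the protocol's plot of maximum QTcF change by day without declaring it in 11.2, and names no entire-period ECG summary that would keep unscheduled or early-termination ECGs displaced from the by-visit tables (minor)

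*SAP*

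**What the plan says.** **Protocol.**
- Section 8.6.6 makes a firm commitment: "Cumulative distribution plots will be provided for maximum change in QT_cF by day".
- The same section gives a definition: "Treatment-emergent ECG abnormalities are defined as those not present at baseline, or those that worsened after treatment". It names no table that uses it.
- Section 8.6 deals with categorical data from unscheduled times and gives ECG finding categories as its example. Such data "will not be included in summaries by time point but will be included in summaries of findings during the entire treatment period".
- Section 8.1 sets the rule for departures: "Any changes to the data summaries and analyses outlined in this section will be described in the applicable SAP".

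**SAP.** Section 9.6 plans summary statistics of values and changes, a full ECG listing, a special QTcF listing and three categorical summaries:
- the investigator's assessment, by visit;
- QTcF Normal/Borderline/Prolonged, with no time frame stated;
- "The number of subjects with absolute ECG values and changes from baseline in the ranges shown in" Table 10, by visit.

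Section 6 states that "unless noted otherwise, only data from visits (scheduled or unscheduled) that fall within analysis windows will be included in summaries". Section 6.5.1 says that, in general, when several valid records exist the one nearest the nominal time is used. Section 11.2 lists three changes: smoking subgroups removed, norepinephrine subgroups added, and standing heart rate analyses added to the orthostatic test. None concerns ECGs.

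**The concern.** Safety and tolerability is a primary objective. Protocol 1.2.2 reports hERG inhibition (IC50 0.95 µM), and protocol 1.4 names increased heart rate as an important potential risk. Neither is a clinical QT signal, but both are reasons to deliver the ECG outputs that were planned.

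The plot is the only planned output built on each subject's maximum QTcF change. Without it, and without an explicit entire-period or worst-value summary, the ECG tables rest on one retained record per window. An ECG taken because something seemed wrong, or at early termination, is the kind most easily displaced by an on-schedule visit. In addition, no output applies the treatment-emergent definition. For the absolute categories, the tables therefore cannot separate a subject who was already prolonged at baseline from one who became prolonged on treatment.

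**Working it through.** **Step 1: compare the planned outputs.**

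| Protocol item | SAP 9.6 | Declared in 11.2 |
|---|---|---|
| Plot of maximum QTcF change by day (8.6.6, stated as an output) | absent | no |
| Treatment-emergent ECG definition (8.6.6, no table named) | no output uses it | no |
| Entire-period counting of unscheduled ECG categories (8.6, a handling rule) | two of three summaries by visit, third undated | no |

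Only the first row is a named output that has gone. SAP 9.6 and 11.2 show no blacked-out text that could hide it.

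**Step 2: can an ECG drop out of the by-visit tables?**

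Inputs: the SAP Table 3 Week 4 ECG window is Days 2 to 71, nominal Day 28. Day 1 in the SAP is the first dose, which is protocol Day 2. Visit 3 is protocol Day 29 ± 3.
- Window length: 71 − 2 + 1 = 70 days.
- Visit 3 in SAP days: 28 ± 3, so Days 25 to 31, at most 3 days from nominal.
- An ECG on day d always loses when |d − 28| > 3. That is Days 2–24 (23 days) and Days 32–71 (40 days): 23 + 40 = 63 of 70.

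The same holds in the randomized period. It has one ECG window centred on first randomized dose + 41 days, so an earlier ad hoc ECG loses to an on-schedule Visit 9.

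**Step 3: which ECGs are exposed?**
- Scheduled open-label ECGs fall on protocol Days 1, 29 and 113, so none falls on the 63 days. In this window only ad hoc ECGs, and early-termination ECGs on Days 32–71, are exposed. The documents do not give their number.
- From Day 72, an early-termination ECG is kept as the Week 16 record, because no Visit 6 competes with it.
- For Week 4 continuation failures, assume the last dose is on the Visit 3 day. An end-of-study visit a full 14 days later falls on Days 39 to 45. With a half-life of 30 to 40 hours (protocol 1.3.1), 14 days = 336 h. Then 336/40 = 8.4 half-lives (0.5^8.4 = 0.30% left) and 336/30 = 11.2 half-lives (0.5^11.2 = 0.04% left). Keeping their on-drug Visit 3 ECG loses little.

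**Step 4: what remains uncovered?** Table 10 has seven columns. Three are changes from baseline (HR, PR %, QTcF) and four are absolute (HR, PR, QRS, QTcF). The gap is a displaced threshold crossing that was not reported as an adverse event, and the missing within-subject baseline split for the four absolute columns.

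**The case against.** The strongest reply is that only the plot is a removed protocol output. A reader might infer that the SAP dropped three promised ECG analyses. The documents do not support that: the treatment-emergent text is a definition with no table attached, and protocol 8.6 is a data-handling rule that presupposes entire-period summaries without specifying an ECG one. Protocol 8.6 also says unscheduled quantitative data are only listed, so its entire-period rule reaches numeric thresholds only if those are treated as categories. The undated QTcF summary could be produced for the whole period. SAP 6 does describe how unscheduled data are handled, and protocol 8.1 asks for changes to be described in the SAP, not in 11.2 specifically.

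A reader might also infer that the SAP contradicts the protocol on the special listing. The protocol offers, as an example, "values of QT_cF ≥450 msec if male or ≥470 msec if female, QT_cF increases from baseline >60 msec"; the SAP plans "A separate listing of data for subjects with postbaseline values of QTcF ≥ 500 msec or a QTcF increase from baseline > 60 msec". The protocol leaves these limits to the SAP, so this is a choice the SAP was entitled to make.

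Finally, a plot by day may largely repeat the change statistics and the Table 10 QTcF-change column.

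All of this stands and limits the point. It does not explain the missing plot: redundancy could justify removing it, but the removal is described nowhere in the readable SAP. Nor does it name a summary in which a displaced ECG is sure to be counted.

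**Conclusion.** The point holds as a minor one. One descriptive safety output promised in the protocol is missing and undeclared. Separately, no ECG summary is explicitly entire-period, so unscheduled or early-termination ECGs can leave the by-visit tables, and the treatment-emergent definition goes unused.

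The size is limited. The 63 of 70 days describes how the window rule works; it does not estimate the ECGs lost, and that number is unknown. A reader might infer that a cardiac signal could be hidden. The documents do not support that. Symptomatic or clinically significant ECG findings must be recorded as adverse events (protocol 7.2), arrhythmia is an event of special interest (7.1.4), SAP 9.1 summarizes both by period, and every ECG is listed. The practical exposure is mainly in the single-arm open-label period.

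This rests on three assumptions: Visit 3 occurs within its ± 3 days, the general closest-record rule is applied to ECGs, and no output outside the published text fills the gap.

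**What to change.** 1. In SAP 9.6, restore the cumulative distribution plot of maximum QTcF change by day, or list its removal in 11.2.
2. Add one table per period of baseline to worst postbaseline value for QTcF category and for the PR, QRS and HR thresholds. Apply the protocol's treatment-emergent definition and include unscheduled and early-termination ECGs. The layout is a proposal; SAP 9.4 already uses shift tables for laboratory data.
   - For subjects who continue to randomization, end the open-label period at the first randomized dose. Otherwise ECGs taken after randomization, possibly on placebo, would count as open-label.
   - Use last dose plus 14 days only for open-label discontinuers and for the randomized period, in keeping with the distinction in protocol 8.6.2.
   - Footnote that baseline is on drug for the randomized period and for subjects rolling over from ampreloxetine in Study 0169.

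Lowering the special listing to the Prolonged cutoffs (QTcF ≥450 msec in men, ≥470 msec in women) is optional and is not a correction.

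The cost is SAP wording, one plot and one table per period, all from ECGs already collected. The downside is that some transient or off-drug readings will be counted in a worst-value table. No efficacy analysis changes.
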